7.0 Protocol Deviations

AbbVie does not allow intentional/prospective deviations from the protocol, except when necessary to eliminate an immediate hazard to study subjects. The principal investigator is responsible for complying with all protocol requirements, and applicable global and local laws regarding protocol deviations. If a protocol deviation occurs (or is identified) after a subject has been enrolled, the principal investigator is responsible for notifying Independent Ethics Committee (IEC)/Independent Review Board (IRB) regulatory authorities (as applicable), and the following AbbVie Clinical Contacts:

Primary Contact:

Alternate Contact:

Such contact must be made as soon as possible to permit a review by AbbVie to determine the impact of the deviation on the subject and/or the study. Any significant protocol deviations affecting subject eligibility and/or safety must be reviewed and/or approved by the IEC/IRB and regulatory authorizes, as applicable, prior to implementation.

8.0 Statistical Methods and Determination of Sample Size

8.1 Statistical and Analytical Plans

An interim analysis will occur after all enrolled subjects have completed through Post-Treatment Week 12 or prematurely discontinued from the study. The database will be versioned after performing appropriate data cleaning. Final data through Post-Treatment Week 48 will be locked in a later version of the database after appropriate data cleaning is performed.

SAS® (SAS Institute, Inc., Cary, NC) for the UNIX operating system will be used for all analyses. The intent-to-treat (ITT) population will consist of all enrolled subjects who received at least one dose of study drug. Efficacy, safety, and demographic analyses will be performed on all subjects in the ITT population.

Detailed statistical methods for all endpoints will be provided in the Statistical Analysis Plan (SAP).

No data will be imputed for any efficacy or safety analyses except for analyses of the HCV RNA endpoints.

HCV RNA values will be selected for the SVR₁₂ analysis based on defined visit windows. When there is no HCV RNA value in a visit window based on defined visit windows, the closest values before and after the window, regardless of the value chosen for the subsequent and preceding window, will be used for the flanking imputation described below.

If a subject has a missing HCV RNA value at a post-Day 1 visit, but with undetectable or unquantifiable HCV RNA levels at both the preceding value and succeeding value, the HCV RNA level will be considered undetectable or unquantifiable, respectively, at this visit for this subject. For SVR₁₂ analysis, if there is no value in the appropriate window but there is an HCV RNA value after the window, then it will be imputed into the SVR₁₂ window. Subsequent to this imputation, if a subject is missing a value for the visit window associated with the analysis, the subject will be imputed as a visit failure (i.e., not undetectable or unquantifiable).

8.1.1 Demographics

Demographics and baseline characteristics will be summarized by treatment arm for all subjects in the ITT population. Demographics include age, weight, height, and BMI as continuous variables, and sex, race, age category ([< 55 years or ≥ 55 years] and [< 65 or ≥ 65 years]), and BMI category (< 30 kg/m² or ≥ 30 kg/m²). Baseline characteristics will include: IL28B genotype ([CC, CT, or TT] and [CC or non-CC]), prior treatment history (treatment naïve, pegIFN/RBV null-responder, pegIFN/RBV partial responder, SOF breakthrough/nonresponder, HCV therapy relapser, HCV relapse/breakthrough, HCV therapy nonresponder, pegIFN intolerant, and pegIFN experienced), baseline HCV RNA levels ([continuous] and [< 800,000 IU/mL or ≥ 800,000 IU/mL]), and HCV subgenotype (3, 3a, 3b, or 3c). Summary statistics (N, mean, median, standard deviation [SD], and range) will be generated for continuous variables (e.g., age and BMI). The number and percentage of subjects will be presented for categorical variables (e.g., sex and race).

8.1.2 Efficacy

All efficacy analyses will be performed on the ITT population. Plasma HCV RNA levels will be determined for each sample collected by the central laboratory using the Roche COBAS TaqMan® real-time reverse transcriptase-PCR (RT-PCR) assay v. 2.0. The lower limit of detection (LLOD) is 20 IU/mL and results below LLOD are reported as "HCV RNA not detected;" the LLOQ for this assay is 25 IU/mL and results below LLOQ but detectable are reported as "< 25 IU/mL HCV RNA detected."

8.1.2.1 Primary Efficacy Endpoint

The primary endpoint is the percentage of subjects with SVR₁₂ (HCV RNA < LLOQ 12 weeks after the last actual dose of study drugs). The number and percentage of subjects achieving SVR₁₂ will be calculated for each treatment arm and 2-sided 95% Wilson score confidence intervals for a binomial proportion will be computed.

8.1.2.2 Secondary Efficacy Endpoints

The secondary efficacy endpoints are:

- The percentage of subjects in each treatment arm and across all treatment arms with on-treatment virologic failure (rebound defined as confirmed HCV RNA \geq LLOQ after HCV RNA < LLOQ during treatment, or confirmed increase from nadir in HCV RNA at any time point during treatment, or failure to suppress during treatment (all on-treatment values of HCV RNA \geq LLOQ) with at least 6 weeks (defined as active study drug duration \geq 36 days) of treatment.
- The percentage of subjects with post-treatment relapse (relapse₁₂ defined as confirmed HCV RNA \geq LLOQ between end of treatment and 12 weeks after last actual dose of active study drug (up to and including the SVR₁₂ assessment time point) for a subject with HCV RNA < LLOQ at Final Treatment Visit who completes treatment. Completion of treatment is defined as study drug duration \geq 77 days.

The numbers and percentages of the subjects with virologic failure during treatment and with post-treatment relapse will be calculated for each arm. The corresponding 2-sided 95% Wilson score confidence intervals for a binomial proportion will be calculated.

8.1.2.3 Additional Efficacy Endpoints

The following additional efficacy endpoints will be summarized and analyzed for each treatment arm:

- All reasons for not achieving SVR₁₂ for subjects who do not achieve SVR₁₂;
- Number and percentage with unquantifiable HCV RNA at each post-baseline visit throughout the Treatment Period (using data from the central laboratory as observed, i.e., no imputation for missing data);
- The percentage of subjects with HCV RNA < LLOQ 24 weeks after the last actual dose of study drug (SVR₂₄);
- All reasons for not achieving SVR₂₄ for subjects who do not achieve SVR₂₄.
- Time to suppression of HCV RNA (defined as the study day of the first of two successive HCV RNA < LLOQ) during the Treatment Period.

In the above analyses that use the number and percentage of responders, the rates and 2-sided 95% Wilson score confidence interval for a binomial proportion will be calculated. For HCV RNA levels, the time to suppression during treatment will be calculated for each subject, and the median time will be estimated using Kaplan-Meier methodology for right censored observations.

8.1.3 Patient Reported Outcomes

The following exploratory analyses of patient reported outcomes (PROs) will be performed:

- mean change from baseline in EQ-5D-5L health index score and its VAS score to each applicable post-baseline time point
- mean change from baseline in the FSS score and its VAFS score to each applicable post-baseline time point

Summary statistics (n, mean, SD, median, minimum and maximum) at each visit and for change from baseline to each visit will be provided for the EQ-5D-5L health index and its VAS scores, and the FSS and its VAFS scores.

Additional analyses of PROs will be performed as useful and appropriate.

8.1.4 Resistance Analyses

The genes of interest for population sequencing in this study are those encoding full length NS3/4A, NS5A, and NS5B. For clonal sequencing, the DNA encoding NS3 amino acids 1 – 181, NS5A amino acids 1 – 215, and NS5B amino acids 280 – 591 will be sequenced. Amino acid positions where resistance-associated variants have been identified in vitro and/or in vivo in genotype 3 are 56, 80, 155, 156, 166, and 168 in NS3 for ABT-450; 28, 30, 31, 32, 58, and 93 in NS5A for ombitasvir; and 282 in NS5B for sofosbuvir.

Only samples with an HCV RNA level of \geq 1,000 IU/mL will undergo sequence analysis in order to allow accurate assessment of products of amplification. Therefore if the HCV RNA level at the time of virologic failure or treatment discontinuation is $<$ 1,000 IU/mL, the sample closest in time after the failure/discontinuation with an HCV RNA level \geq 1,000 IU/mL will be used. Included time points for analyses on samples from subjects who do not achieve SVR₁₂ are: 1) time of virologic failure/treatment discontinuation or sample closest in time after failure/discontinuation with an HCV RNA level of \geq 1,000 IU/mL, 2) 24 weeks post-DAA treatment, provided that resistance-associated variants were detected by either population or clonal sequencing at the time of failure/discontinuation, and 3) 48 weeks post-DAA treatment, provided that resistance-associated variants were detected by either population or clonal sequencing at 24 weeks post-DAA treatment. For these samples, clonal sequencing of a given target will be performed only if no variants are detected at signature resistance-associated amino acid positions by population sequencing. In addition, clonal sequencing may be performed if there is a complex mixture of amino acids at a signature resistance-associated position that cannot be resolved by population sequencing.

The following definitions will be used in the resistance analyses:

- Baseline variant: a variant (by population sequencing) in a baseline sample determined by comparison of the amino acid sequence of the baseline sample to the appropriate prototypic reference amino acid sequence for a given DAA target.
- Post-baseline variant by population sequencing: an amino acid variant detected by population sequencing in a post-baseline time point sample that was not detected by population sequencing at baseline in the subject.
- Post-baseline variant by clonal sequencing: a variant at a signature resistance-associated amino acid position that was not present in a subject by population sequencing at baseline, but that is detected in a post-baseline sample from that subject by clonal sequencing in at least 2 clones from that sample (among the subset of subjects for whom clonal sequencing is performed).
- Emerged variant by population sequencing: a post-baseline variant that is observed in samples from 2 or more subjects of the same HCV subgenotype by population sequencing.
- Linked variant by population sequencing: 2 or more signature resistance-associated or emerged amino acid variants identified within a target by population sequencing, and no mixture of amino acids is detected at either position.
- Linked variant by clonal sequencing: at least 2 clones from a given sample containing the same 2 or more signature resistance-associated amino acid variants by clonal sequencing.

Baseline samples will be sequenced by population sequencing for all subjects for whom samples are available. A listing by subject of all baseline variants relative to the appropriate prototypic reference sequence at signature resistance-associated amino acid positions will be provided for each DAA target (NS3, NS5A, and NS5B). In addition, a summary of the number and percentage of subjects with each baseline variant at a signature resistance-associated amino acid position within each target by HCV subgenotype out of the total number of baseline samples sequenced will also be provided.

The following analyses will be performed for subjects who do not achieve SVR₁₂ and have post-baseline resistance data available.

The HCV amino acid sequence as determined by population sequencing on the sample closest in time after virologic failure or treatment discontinuation with an HCV RNA level of $\geq 1,000$ IU/mL will be compared to the baseline and appropriate prototypic reference amino acid sequences. Listings by subject of all post-baseline variants detected by population sequencing relative to the baseline amino acid sequences will be provided for each DAA target (NS3, NS5A, and NS5B). Listings by subject of all emerged variants by population sequencing, by amino acid position and variants within a DAA target in a post-baseline sample relative to the baseline amino acid sequence will be provided for each DAA target. In addition, listings by subject of all post-baseline variants (by population sequencing) at signature resistance-associated amino acid positions relative to the appropriate prototypic reference amino acid sequence will be provided for each DAA target (NS3, NS5A, and NS5B).

The number and percentage of subjects with emerged variants by population sequencing by amino acid position and variant within a DAA target at the time of VF compared to baseline will be summarized. The analyses will be grouped by HCV subgenotype and DAA target (NS3, NS5A, or NS5B).

Linkage between emerged or signature variants by population sequencing will also be evaluated. A listing by subject and time point of the linked variants by population sequencing for each target will be provided.

For the subset of samples for which clonal sequencing is performed, a listing of post-baseline variants by clonal sequencing at signature resistance-associated amino acid positions by subject, amino acid position and variant, as well as time point will be provided for each DAA target. Furthermore, listings of the linked variants by clonal sequencing by subject, DAA target, and time point will be provided.

The persistence of post-baseline variants at signature resistance-associated amino acid positions for each target (NS3, NS5A, and NS5B) will be assessed by population and/or clonal sequencing at Post-Treatment Weeks 24 and 48. Listings by subject and time point of all post-baseline variants relative to the baseline amino acid sequence will be provided for each DAA target (NS3, NS5A, and NS5B). Additionally, the number and percent of subjects in whom an emerged variant persists at Post-Treatment Weeks 24 or 48 out of the total number of subjects with that emerged variant at the failure/discontinuation time point and at Post-Treatment Week 24 and/or Post-Treatment Week 48 will be summarized by HCV subgenotype, DAA target, and variant.

Replicon EC₅₀ values may not be obtainable for all samples, but for samples where phenotype data is obtained, the fold change in EC₅₀ level at each post-baseline time point where phenotypic analysis was performed will be determined relative to the EC₅₀ level of baseline and of prototypic standard.

8.1.5 Safety

All subjects who receive at least one dose of study drug will be included in the safety analyses.

8.1.5.1 Adverse Events

Adverse events will be coded using the Medical Dictionary for Regulatory Activities (MedDRA).²⁴ The number and percentage of subjects with treatment-emergent adverse events (i.e., any event that begins or worsens in severity after initiation of study drug through 30 days post-study drug dosing) will be tabulated by primary MedDRA System Organ Class (SOC) and preferred term (PT) for each treatment arm and overall. The tabulation of the number of subjects with treatment-emergent adverse events by severity rating and relationship to study drug will also be provided. Subjects reporting more than one adverse event for a given MedDRA preferred term will be counted only once for that term using the most severe incident for the severity rating table and the most related for the relationship to study drug table. Subjects reporting more than one type of event within a SOC will be counted only once for that SOC.

Additional analyses will be performed if useful and appropriate.

8.1.5.2 Clinical Laboratory Data

Clinical laboratory tests will be summarized at each visit. The baseline value will be the last measurement prior to the initial dose of study drug. Mean changes from baseline to each Post-Baseline Visit will be summarized descriptively for each treatment arm.

Laboratory data values collected during the Treatment Period will be categorized as low, normal, or high based on reference ranges of the laboratory used in this study. The number and percent of subjects who experience post-baseline shifts during treatment in clinical laboratory values from low/normal to high and high/normal to low based on the normal range will be summarized for each treatment arm.

In addition, the number and percentage of subjects with post-baseline values meeting pre-specified criteria for Potentially Clinically Significant laboratory values during treatment will be summarized for each arm. Additional analyses will be performed if useful and appropriate.

8.1.5.3 Vital Signs Data

Vital sign measurements will be summarized at each visit during the treatment period. Mean changes in temperature, systolic and diastolic blood pressure, pulse, and weight from baseline to each Post-Baseline Visit will be summarized descriptively for each treatment arm. The baseline value will be the last measurement prior to the initial dose of study drugs. Frequencies and percentages of subjects with post-baseline values meeting pre-defined criteria for Potentially Clinically Significant vital signs values during treatment will be summarized for each treatment arm.

8.1.6 Pharmacokinetic and Exposure-Response Analyses

Individual plasma concentrations of ABT-450, ritonavir, ombitasvir, SOF, GS-581007, and RBV will be tabulated and summarized. Individual plasma concentrations of possible

metabolites of ABT-450, ombitasvir, and SOF (other than GS-331007) may be tabulated and summarized if measured and sufficient levels of metabolites are observed.

Values for the pharmacokinetic parameters of ABT-450, ombitasvir, ritonavir, SOF, GS-331007, and RBV including the C_{\max} , T_{\max} , C_{trough} , and AUC will be summarized and tabulated. Plasma concentration data from this study may be combined with data from other studies and analyzed using the following general methodology. Population pharmacokinetic analyses will be performed using a nonlinear mixed-effects modeling (NONMEM) software (Version VI or higher). The structure of the starting pharmacokinetic model will be based on the pharmacokinetic analysis of data from previous studies. Apparent oral clearance (CL/F) and apparent volume of distribution (V/F) of the PK analytes will be the pharmacokinetic parameters of interest in the analysis. If the estimation of the parameters describing absorption characteristics is not possible then they will be fixed to the values obtained from previous analysis. The evaluation criteria described below will be used to examine the performance of different models.

- Model discrimination will be assessed by a likelihood ratio test comparing objective function values (OFVs) when two competing models are compared. An OFV difference (ΔOFV) of 3.84 will be considered to be significant (χ^2 , $p < 0.05$) when two nested models with a difference of one parameter ($df = 1$) are compared. The Akaike's information criterion (AIC) will be used to compare non-nested models.
- Various goodness-of-fit criteria, including diagnostic scatter plots and individual plots of model fits.
- Visual predictive checks or standardized visual predictive checks.
- Plausibility of parameter estimates and precision of parameter estimates.

Covariate-parameter relationships will be tested based on scientific principles or prior knowledge i.e., only physiologically relevant or clinically meaningful covariates (such as subject age, sex, body weight, concomitant medications, laboratory markers of hepatic or renal function, etc.) will be explored. Covariate modeling will also be guided by plots of

posterior Bayesian estimates of pharmacokinetic parameters versus covariates (delta plots) or plots of η versus covariates (eta plots). If needed, a generalized additive method (GAM) or another suitable regression/smoothing method may be employed for covariate selection. Several covariate models (linear or nonlinear mathematical functions) will be explored to adequately describe the pharmacokinetic data. A likelihood ratio test will be employed for covariate selection by comparing OFVs obtained from NONMEM. A decrease in the OFV of at least 3.84 ($\chi^2, p < 0.05, df = 1$) is considered significant in the univariate analysis. A full model will be developed with all significant covariates from the univariate analysis. Finally, backward elimination will be performed to develop a final model. An increase in the OFV of at least 7.88 ($\chi^2, p < 0.005, df = 1$) will be considered significant in the backward elimination. The AIC will be used to compare non-nested models.

Relationship between exposure and clinical observations (antiviral activity) will be explored. Exposure-response relationships for primary and secondary efficacy variables and/or some safety measures of interest may also be explored.

The relationship between exposure (e.g., population pharmacokinetic model predicted concentrations over time or average concentrations or AUC or trough concentrations of the individual model-predicted pharmacokinetic profiles, or some other appropriate measure of exposure) and antiviral activity will be explored. Exposure response relationships will be explored using a semi-mechanistic viral dynamic model and/or logistic regression analyses.

The viral dynamic model will account for target cell growth and death, infection of target cells, infected cell infection and death rate, production of virus by infected cells, and inhibition of production of virus by the various DAs. Effect of RBV will be explored on infection of target cells by virus. Models will explore mutation of the wild type to single and/or double mutant species depending on the available clinical resistance data.

Additional adjustments to the structural and error models will be made during model development as appropriate.

Logistic regression analyses will explore the relationship between exposure and one or more virologic endpoints (e.g., RVR, EVR, SVR₄, SVR₁₂, relapse following end of treatment and breakthrough on treatment).

Additionally, relationships between exposure and safety endpoints of interest may be explored.

8.2 Determination of Sample Size

It is planned to enroll approximately 20 subjects into this study. With a sample size of 10 subjects per arm and an observed SVR₁₂ rate of 90%, the 2-sided 95% confidence interval, using Wilson's score confidence interval, will be (59.6%, 98.2%). Subjects who do not have data at PT Week 12 (after performing the described imputation) count as failures for SVR₁₂ so no adjustment for dropout is applicable.

From the perspective of safety assessment, the probability that a given adverse event would not be observed among 20 subjects is shown in the second column of [Table 11](#) for various true population incidence rates. With 20 subjects, the probability is at least 97.8% to observe an adverse event with an incidence rate of 10% or higher.

Table 11. Probability of Not Observing an Adverse Event or Lab Abnormality for Various True Incidence Rates

True Incidence Rate	Probability of Not Observing
0.10	0.122
0.20	0.012
0.30	< 0.001
0.40	< 0.001
0.50	< 0.001

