4.3 Sample Size

It is planned to enroll approximately 70 subjects into this study. With a sample size of 10 subjects per arm and an observed SVR₁₂ rate of 90%, the 2-sided 95% confidence

interval, using Wilson's score confidence interval, will be (59.6%, 98.2%); With a sample size of 20 subjects per arm and an observed SVR₁₂ rate of 90%, the 2-sided 95% confidence interval, using Wilson's score confidence interval, will be (69.9%, 97.2%). Subjects who do not have data at PT Week 12 (after performing the described imputation) count as failures for SVR₁₂ so no adjustment for dropout is applicable.

From the perspective of safety assessment, the probability that a given adverse event would not be observed among 70 subjects is shown in the second column of [Table 1](#) for various true population incidence rates. With 70 subjects, the probability is at least 99.9% to observe an adverse event with an incidence rate of 10% or higher.

Table 1. Probability of Not Observing an Adverse Event or Lab Abnormality with 70 Subjects for Various True Incidence Rates

True Incidence Rate	Probability of Not Observing
0.10	< 0.001
0.20	< 0.001
0.30	< 0.001
0.40	< 0.001
0.50	< 0.001

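### Protocol 8.2 claims at least a 97.8% chance of seeing a 10%-incidence adverse event in 20 subjects; its own Table 11 implies 87.8%

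*Protocol*

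**What the plan says.** Protocol section 8.2 plans for about 20 subjects: "It is planned to enroll approximately 20 subjects into this study". It then turns to safety and says that "the probability that a given adverse event would not be observed among 20 subjects is shown in the second column of" Table 11, which is titled "Probability of Not Observing an Adverse Event or Lab Abnormality for Various True Incidence Rates". The first row of that table gives 0.122 at a true incidence of 0.10. The second row gives 0.012 at 0.20, and the three remaining rows are all below 0.001.

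The sentence just before the table sums this up in words: "With 20 subjects, the probability is at least 97.8% to observe an adverse event with an incidence rate of 10% or higher".

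SAP section 4.3 has a parallel paragraph for the later six-arm design: "With 70 subjects, the probability is at least 99.9% to observe an adverse event with an incidence rate of 10% or higher". It neither repeats nor corrects the 20-subject figure.

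**The concern.** The sentence and the first row of the table describe the same quantity from opposite sides: the probability of observing an event and of not observing it, at the same incidence and the same number of subjects. They should add to one. They add to 0.978 + 0.122 = 1.100, so one of them must be wrong.

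Safety is one of the study's primary objectives, and Protocol section 3.2 notes that the AbbVie agents and sofosbuvir have not previously been given together to HCV-infected subjects. The sentence is the protocol's only statement in words of what 20 subjects can reveal about adverse events. A reader who takes it at face value, an ethics committee member for instance, would think a 10%-incidence event almost certain to appear.

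**Working it through.** **Inputs, all from Protocol section 8.2**

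- Number of subjects: n = 20.
- Lowest true incidence covered by the sentence: p = 0.10.
- Stated probability of observing the event: at least 0.978.
- Table 11, probability of not observing it at p = 0.10: 0.122.

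**Formula.** With independent subjects who share a common incidence p, P(no event) = (1 − p)^n and P(at least one event) = 1 − (1 − p)^n.

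**Step 1: reproduce Table 11 with n = 20**

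| True incidence | (1 − p)^20 | Table 11 |
|---|---|---|
| 0.10 | 0.1216 | 0.122 |
| 0.20 | 0.0115 | 0.012 |
| 0.30 | 0.0008 | < 0.001 |
| 0.40 | 0.00004 | < 0.001 |
| 0.50 | 0.000001 | < 0.001 |

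Every row agrees.

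**Step 2: test the sentence.** At p = 0.10, 1 − 0.9^20 = 1 − 0.1216 = 0.8784, or 87.8%. The stated 97.8% does not reproduce.

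**Step 3: look for a reading that gives 97.8%**

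- *At least.* The probability rises with p, so its minimum over incidences of 10% or more is the value at exactly 10%, which is 87.8%. With 20 subjects, 97.8% is first reached at p = 1 − 0.022^(1/20) = 0.174. The sentence is therefore false for true incidences from 10% to about 17.4%. For example, 12% gives 1 − 0.88^20 = 92.2%, and 15% gives 1 − 0.85^20 = 96.1%.
- *Approximately 20.* 18 subjects give 1 − 0.9^18 = 85.0%, and 22 give 1 − 0.9^22 = 90.2%.
- One arm only, n = 10: 1 − 0.9^10 = 65.1%, which is further away.
- Poisson approximation: 1 − e^(−2) = 86.5%.
- At least two events instead of one: 60.8%.
- A different n: ln(0.022)/ln(0.9) = 36.2. At 10% incidence, 36 subjects give 97.7% and 37 give 98.0%, so 37 would be needed.

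None of these readings gives 97.8% with 20 subjects.

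**Step 4: check the neighbouring figures.** The Wilson interval in the same section, for 9 responders out of 10, reproduces as (59.6%, 98.2%). In SAP section 4.3, 0.9^70 = 0.0006, so its 99.9% is correct. Among these figures, the error is confined to the one number.

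**The case against.** The strongest reply concerns weight, since the figure itself cannot be defended. Nothing operative depends on it. The sample size is not derived from a detection probability, enrolment is stopped for safety on ongoing data review (Protocol section 5.4.1.2) with no probability threshold, and the safety analyses are descriptive. The correct 0.122 is printed just below. The two figures differ in one digit, which suggests a typing slip, although that is an inference. The SAP has moved to about 70 subjects with a correct statement of its own, so the analysis plan does not carry the error forward.

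All of that stands and limits the consequence. It does not make the sentence true. The protocol still contains it, and the SAP paragraph addresses a different number of subjects without correcting it.

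One might also question whether 20 is the right denominator, because the SAP's general safety section summarises by arm. The sentence and the introduction to Table 11 both specify 20, and Protocol section 8.1.5.1 tabulates adverse events by "preferred term (PT) for each treatment arm and overall". Using a single arm of 10 would in any case lower the probability, to 65.1%.

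**Conclusion.** The concern holds. For 20 subjects and a true incidence of 10%, the probability of observing the event at least once is 87.8%, and the protocol states 97.8%. The overstatement is 10 percentage points. The chance of missing the event is 12.2% where the sentence implies 2.2%, a ratio of 0.1216/0.022 = 5.5.

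This rests only on the protocol's own n and incidence and on the binomial model that generates Table 11. No outside figure is needed. It is a wrong stated probability that contradicts its own table, it favours the study, and it should be corrected. It does not show that the sample size is inadequate, and it affects no analysis.

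**What to change.** In Protocol section 8.2, change 97.8% to 87.8%. If a later protocol version keeps the 20-subject sentence, make the same change there. Leave Table 11, the planned enrolment and SAP section 4.3 unchanged.

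The cost is one figure in one sentence, with no change to design, analysis or number of subjects. The stated detection probability becomes less favourable, and the sentence then agrees with the table below it.
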